6.2 Subject Exclusion Criteria

Target Disease Exceptions

- Active brain metastases (untreated brain metastases or growth on imaging as defined below) or leptomeningeal disease are not allowed. Subjects with brain metastases are eligible if these have been treated and there is no MRI (or CT if MRI contraindicated) evidence of progression for at least 8 weeks after treatment for these metastases is complete and within 28 days prior to first study treatment.
- Histologically confirmed non-squamous histologies are not allowed; an exception is made for WHO Type I-III nasopharynx histologies.

Medical History and Concurrent Diseases:

- Any medical disorder that, in the opinion of the investigator, might increase the risk associated with study participation or interferes with the interpretation of study results.
- Prior active malignancy within the previous 3 years except for locally curable cancers such as basal or squamous skin cancer, superficial bladder, low risk prostate cancer, breast, or cervix cancer. If other prior malignancy was active within prior 3 years, enrollment requires approval of a principal investigator.
- Patients should be excluded if they have an active, known or suspected autoimmune disease. Subjects are permitted to enroll if they have vitiligo, type I diabetes mellitus, residual hypothyroidism due to autoimmune condition only requiring hormone replacement, psoriasis not requiring systemic treatment, or conditions not expected to recur in the absence of an external trigger
- Subjects with a condition requiring systemic treatment with either corticosteroids (> 10 mg daily prednisone equivalents) or other immunosuppressive medications within 14 days of study drug administration should be excluded. Inhaled or topical steroids and adrenal replacement doses >10mg daily prednisone equivalents are permitted in the absence of active autoimmune disease.

- As there is potential for hepatic toxicity with Nivolumab, drugs with a predisposition to hepatotoxicity should be used with caution in patients treated with Nivolumab-containing regimen.
- Prior treatment with an anti-PD-1, anti-PD-L1, or anti-PD-L2 antibody.
 - NB-patients who have received prior anti-CTLA-4 antibody therapy are eligible assuming such therapy was discontinued within 28 days of enrollment.
- Treatment with any chemotherapy, radiation therapy, biologics for cancer, or investigational therapy within 14 days of randomization.

Physical and Laboratory Test Findings

- Positive test for hepatitis B virus surface antigen or hepatitis C virus ribonucleic acid indicating acute or chronic infection.
- Known history of testing positive for HIV or known AIDS.
- Any grade 4 laboratory abnormalities.

Allergies and Adverse Drug Reaction

- History of allergy to Nivolumab components
- History of severe hypersensitivity reaction to any monoclonal antibody.

Prohibited or Restricted Treatments

The following medications are prohibited during the study:

- Immunosuppressive agents (except to treat a drug-related adverse event).
- Systemic corticosteroids > 10 mg daily prednisone equivalent save for exclusion outlined in the below paragraphs.
- Any concurrent chemotherapy, hormonal therapy, immunotherapy, or investigational agents for treatment of cancer.

Supportive care for disease-related symptoms may be offered to all subjects on the trial.

Permitted Therapies During Study

In either arm, if the investigator deems it medically necessary, non-target lesions can receive conventionally dosed, palliative radiation therapy. Palliative radiotherapy is not permitted within 24 weeks of first study treatment. Subjects receiving palliative radiation therapy will be considered to have had unequivocal progression of disease. Administration of Nivolumab to subjects who received palliative radiation should follow guidelines specified for treatment beyond disease progression. Any subsequent responses to therapy after the receipt of palliative radiation will not be counted towards the calculation of the primary endpoint, but patients who receive palliative radiation who remain on Nivolumab will have continued study-mandated scans until a 2nd progression event or 96 weeks, whichever occurs earlier.

Other permitted therapies include topical, ocular, intra-articular intranasal and inhalational corticosteroids. Adrenal replacement steroid doses including doses > 10 mg daily prednisone are also permitted.

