4.1 OVERVIEW OF STUDY DESIGN/INTERVENTION

4.2 Design

This is a randomized (1:1), open label Phase 2 screening trial in subjects ≥ 18 years old with metastatic HNSCC. Subjects will stratified based on viral status (p16+ OPC/EBER+ NPC vs others) and then randomized to either Nivolumab with interdigitated SBRT or Nivolumab alone.

Subjects must undergo screening evaluations to determine eligibility within 28 days prior to randomization.

Sixty (60) subjects will be randomized to one of the following arms:

- Arm 1: Nivolumab 3mg/kg IV every 2 weeks
- Arm 2:
 - Image Guided, Stereotactic Body Radiotherapy (27 Gy over 3 fractions given every other day) to a single lesion to start by study day 14 (study day 1 is day of first dose of Nivolumab).
 - Nivolumab 3mg/kg IV starting day 1 and then every 2 weeks thereafter.
- Treatment with Nivolumab will continue until progression or unacceptable toxicity.

Key Inclusion Criteria:

- 1) Males and females ≥ 18 years of age.
- 2) Eastern Cooperative Oncology Group (ECOG) performance status ≤ 2 .
- 3) Histologically confirmed metastatic HNSCC, including nasopharynx WHO Type I-III histologies; patients can have simultaneous loco-regional disease.
- 4) Subjects must have at least two lesions:
 - One lesion must be safely amenable to irradiation in the opinion of the treating radiation oncologist. This can be a lesion that was previously irradiated as long as prior radiation preceded projected first fraction of SBRT by at least 6 months.
 - At least one, not-to-be-irradiated lesion measurable by CT or MRI per RECIST 1.1 criteria.
- 5) Available formalin fixed, paraffin-embedded (FFPE) tumor tissue block with unstained slides of tumor sample obtained via excisional, incisional, or core needle biopsy from a loco-regionally recurrent or metastatic lesion; FFPE tumor tissue block with unstained slides from the primary disease is acceptable with approval of principal investigator.
- 6) Documentation of tumor viral status (p16 testing for oropharynx, EBER for nasopharynx). Tests done on primary tumor specimens at outside institutions are sufficient to meet this criterion.
- 7) Prior palliative or curative radiotherapy must be completed at least 14 days prior to randomization.

Key Exclusion Criteria:

- 1) Active brain metastases or leptomeningeal metastases are not allowed.
- 2) Non-squamous histologies are not allowed; an exception is made for WHO Type I-III nasopharynx histologies.

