- 3) Prior treatment with an anti-PD-1, anti-PD-L1, anti-PD-L2 antibody.
- 4) Prior active malignancy within the previous 3 years except for locally curable cancers such as basal or squamous skin cancer, superficial bladder, low risk prostate cancer, breast, or cervix cancer. If other prior malignancy was active within prior 3 years, enrollment requires approval of a principal investigator.
- 5) Subjects with active, known or suspected auto-immune disease. Subjects with vitiligo, type 1 diabetes mellitus, residual hypothyroidism due to autoimmune condition only requiring hormone replacement, psoriasis not requiring systemic treatment, or conditions not expected to recur in the absence of an external trigger are eligible to enroll.
- 6) Subjects with a condition requiring systemic treatment with either corticosteroids (> 10 mg daily prednisone equivalents) or other immunosuppressive medications within 14 days of study drug administration. Inhaled or topical steroids and adrenal replacement doses >10 mg daily prednisone equivalents are permitted in the absence of active autoimmune disease.

Based upon an estimated ORR of 15% in the Nivolumab alone arm in a PD-L1 unselected population and an ORR of 45% in the Nivolumab and SBRT arm, the enrollment of 54 patients will provide a one-sided alpha of 0.10 and a power of 0.80. Assuming a 10% drop-out rate, we will seek to enroll 60 patients. Patients will be randomized to the two

treatment arms in a 1:1 ratio (30 subjects in Arm 1 and 30 subjects in Arm 2). Patients will be stratified based upon viral status (HPV/EBV+ vs not). ORR will be assessed by the investigator using RECIST 1.1 criteria. Treatment with Nivolumab will continue until RECIST 1.1-defined progression, unacceptable toxicity, or withdrawal of consent. Nivolumab dose reductions will not be allowed.

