6.2 Subject Inclusion Criteria

1) Signed Written Informed Consent

- Subjects must have signed and dated an IRB/IEC approved written informed consent form in accordance with regulatory and institutional guidelines.
- Subjects must be willing and able to comply with scheduled visits, treatment schedule, laboratory testing, and other study obligations.

2) Target Population

- Males and females ≥ 18 years of age.
- Eastern Cooperative Oncology Group (ECOG) performance status ≤ 2 .
- Histologically confirmed metastatic HNSCC, including nasopharynx WHO Type I-III histologies; patients can have simultaneous loco-regional disease. Central biopsy review at MSKCC is not required.
- Subjects must have at least two lesions:
 - At least one lesion must be safely amenable to irradiation and likely to meet criteria delineated in Section 9.2.1 in the judgment of the treating radiation oncologist. This can be a lesion that was previously irradiated as long as prior radiation was at least 6 months prior to projected first fraction of SBRT and as long as reirradiation dose constraints as outlined in appendix are being met.
 - A separate, not-to-be-irradiated lesion measurable by CT or MRI per RECIST 1.1 criteria.
- A formalin fixed, paraffin-embedded (FFPE) tumor tissue block or a minimum of 3 unstained slides of tumor sample obtained via excisional, incisional, or core needle biopsy from a metastatic or loco-regionally recurrent lesion. A new baseline biopsy does not need to be obtained for study purposes. If 3 unstained are unavailable from

a metastatic or loco-regionally recurrent lesion, with permission of the PI, FFPE tumor tissue from the primary disease site at the time of original diagnosis is acceptable.

- For oropharynx or nasopharynx primary lesions, documentation of viral status is required (e.g. high risk HPV sub-type PCR, p16 IHC, HPV ISH, EBER, etc). Tests done on primary tumor specimens from date of initial diagnosis at outside institutions are sufficient to meet this criterion.
- Prior palliative or curative radiotherapy must be completed at least 14 days prior to randomization.
- Immunosuppressive doses of systemic medication, such as steroids or absorbed topical steroids (doses >10mg/day prednisone or equivalent) must be discontinued at least 14 days prior to first Nivolumab administration.
- Screening laboratory values must meet the following criteria (using CTCAE v4.0) and should be obtained within 28 days prior to randomization:

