15.3 Randomization

Patients will be randomized to the Nivolumab and SBRT arm or Nivolumab only arm. For patients enrolled, immediately after consent is obtained, the RSA at MSKCC will register participants in the Protocol Participant Registration (PPR) system. Once the participant's eligibility is established the registration will be finalized and the participants will be randomized using the Clinical Research Database (CRDB). Randomization will be accomplished by the method of random permuted block, and will be stratified by viral status (positive or negative). After treatment arm is determined by randomization, RSAs will notify the physicians at MSKCC of the treatment arm and participant ID via email within 24 hours of randomization. All Data will be collected and analyzed at MSKCC. Compiled data will be submitted to the biostatistician on study ([name]) for analysis.

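### The anti-CTLA-4 note sets a 28-day maximum since stopping therapy, where the protocol's other prior-therapy rules set minimum washouts

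*Combined protocol and SAP*

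**What the plan says.** The sentence is a sub-bullet in Section 6.2 Subject Exclusion Criteria, under the exclusion of prior anti-PD-1, anti-PD-L1 or anti-PD-L2 antibodies. It says that patients previously given an anti-CTLA-4 antibody are "eligible assuming such therapy was discontinued within 28 days of enrollment".

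The rules around it are:

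- The next bullet in the same list excludes "Treatment with any chemotherapy, radiation therapy, biologics for cancer, or investigational therapy within 14 days of randomization".
- Section 6.2 Subject Inclusion Criteria states: "Prior palliative or curative radiotherapy must be completed at least 14 days prior to randomization".
- The same section says that immunosuppressive doses of systemic medication "must be discontinued at least 14 days prior to first Nivolumab administration".
- The key exclusion criteria in Section 4.2 Design list "Prior treatment with an anti-PD-1, anti-PD-L1, anti-PD-L2 antibody" and do not mention anti-CTLA-4 therapy.

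On dates, Section 4.2 states: "Subjects must undergo screening evaluations to determine eligibility within 28 days prior to randomization". Section 15.3 Randomization has patients registered right after consent. Only when eligibility is established will "the registration will be finalized and the participants will be randomized" apply.

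**The concern.** A washout is meant to ensure that enough time has passed since an earlier treatment. The note does the reverse. Because it states when a patient is eligible, the word 'within' makes 28 days the longest permitted interval.

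The sentence decides eligibility for anyone with prior anti-CTLA-4 therapy. Staff who apply it literally accept the more recently exposed patients and turn away those longest off therapy. Staff who apply the sensible reading enrol patients against the written criterion, which is a protocol deviation on paper.

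There is a second, smaller difficulty. The note counts from enrolment and the neighbouring biologics rule counts from randomisation, so the two can run from different dates.

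No effect on the toxicity stopping rule or on ORR is claimed. The documents do not describe carry-over from this drug class.

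**Working it through.** The plan gives no figure to reproduce here, so the check compares wording and then counts days.

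**Direction of each rule**

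| Rule | Form | Effect |
|---|---|---|
| Prior radiotherapy, 14 days before randomisation (6.2 Inclusion) | condition to enter, 'at least' | minimum |
| Immunosuppressive doses, 14 days before first nivolumab (6.2 Inclusion) | condition to enter, 'at least' | minimum |
| Earlier radiation to the SBRT lesion, 6 months before first fraction (6.2 Inclusion) | condition to enter, 'at least' | minimum |
| Cancer biologics, 14 days before randomisation (6.2 Exclusion) | reason to exclude, 'within' | minimum |
| Anti-CTLA-4, 28 days before enrolment (6.2 Exclusion) | condition to enter, 'within' | **maximum** |

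The word 'within' produces a minimum washout in an exclusion and a maximum in a condition of eligibility. Only the anti-CTLA-4 note falls in the second group.

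**Joint effect with the biologics exclusion**

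Let d be whole days from stopping anti-CTLA-4 therapy to enrolment, g the days from enrolment to randomisation, and r = d + g the days from stopping to randomisation.

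- Note, read literally: 0 ≤ d ≤ 28, so g ≤ r ≤ 28 + g.
- Biologics exclusion, counting an anti-CTLA-4 antibody as a cancer biologic and day 14 as excluded: r ≥ 15.
- Both together: max(15, g) ≤ r ≤ 28 + g.

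The documents do not give g. A range of 0 to 28 days is assumed, taken from the 28-day screening period. The last column counts admitted days that would fall short of a 28-day minimum before randomisation, if that was the intent (r < 28).

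| g (days) | Admitted r | Days admitted | Of these, r < 28 |
|---|---|---|---|
| 0 | 15–28 | 28 − 15 + 1 = 14 | 27 − 15 + 1 = 13 |
| 7 | 15–35 | 35 − 15 + 1 = 21 | 13 |
| 14 | 15–42 | 42 − 15 + 1 = 28 | 13 |
| 21 | 21–49 | 49 − 21 + 1 = 29 | 27 − 21 + 1 = 7 |
| 28 | 28–56 | 56 − 28 + 1 = 29 | 0 |

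These are calendar days, not patients. The shortfall depends strongly on g, but the ceiling is present in every row: a patient more than 28 + g days off therapy never meets the note's condition. A minimum washout would give r ≥ 28 with no ceiling.

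**The case against.** The strongest reply is that the note bars nobody. It is a clarifying remark under the PD-1/PD-L1/PD-L2 exclusion. No listed exclusion names anti-CTLA-4 therapy, so a patient three months off it triggers none. The 14-day biologics rule then governs, and concurrent immunotherapy is prohibited in any case. On this view the sentence is a drafting slip, with exclusion phrasing carried into a sentence about who is eligible, and its consequence is small. This stands in part: the bar on patients long off therapy is an inference, and no reading permits ongoing anti-CTLA-4 treatment. But if the 28-day condition excludes nobody, it has no function and should be deleted. If it has a function, it works in the wrong direction.

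A second reply is that the protocol often uses enrolment and randomisation interchangeably. Section 4.2, for example, times the end of tumour follow-up from the last enrolment and the ORR analysis from the last randomisation, both at 96 weeks. That weakens the point about different dates. If the two dates coincide, the g = 0 row applies, and there the literal window is at its narrowest.

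Third, the 0 to 28 day range for g is assumed, and a 28-day minimum is nowhere stated as the intent. Both are true. The last column of the table is conditional on that intent; the existence of the ceiling is not.

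Finally, few patients are likely to be affected. The standard treatments for metastatic disease described in Section 3.2 include no anti-CTLA-4 agent. This limits the size of the problem but does not make the sentence correct.

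**Conclusion.** The concern holds. As written, the note makes 28 days a maximum time since stopping anti-CTLA-4 therapy, whereas the prior-therapy intervals compared with it all act as minimums, and no other text corrects it. The biologics exclusion supplies a 14-day floor and leaves the ceiling standing.

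That the wording is reversed can be said with high confidence. That a 28-day minimum was intended is likely but not shown. The consequence is confined to eligibility: a risk of wrongful screen failures or of enrolments that contradict the written criterion, in an unknown and probably small number of patients. It should be corrected because the sentence is an operative criterion, even though no design quantity depends on it.

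**What to change.** Reword the note so that prior anti-CTLA-4 therapy must have been discontinued at least 28 days before randomisation. This uses the same reference date as the biologics exclusion and removes the ceiling. If no longer washout was intended for this class, delete the 28-day condition and let the 14-day exclusion apply. The study team must say which was meant.

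Either choice costs one sentence in Section 6.2 and one line in the eligibility checklist required at registration (Section 15.2). Sample size and analysis stay as they are.

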7.0 RECRUITMENT PLAN

Potential research subjects will be identified by a member of the patient's head and neck treatment team, the site protocol investigator, or research team at Memorial Sloan-Kettering Cancer Center (MSKCC). If the investigator is a member of the treatment team, s/he will screen their patient's medical records for suitable research study participants and discuss the study and their potential for enrolling in the research study. Potential subjects contacted by their treating physician will be referred to the investigator/research staff of the study.

The site principal investigator may also screen the medical records of patients with whom they do not have a treatment relationship for the limited purpose of identifying patients who would be eligible to enroll in the study and to record appropriate contact information in order to approach these patients regarding the possibility of enrolling in the study.

During the initial conversation between the investigator/research staff and the patient, the patient may be asked to provide certain health information that is necessary to the recruitment and enrollment process. The investigator/research staff may also review portions of their medical records at MSKCC in order to further assess eligibility. They will use the information provided by the patient and/or medical record to confirm that the patient is eligible and to contact the patient regarding study enrollment.

In most cases, the initial contact with the prospective subject will be conducted either by the treatment team, investigator or the research staff working in consultation with the treatment team. The recruitment process outlined presents no more than minimal risk to the privacy of the patients who are screened and minimal PHI will be maintained as part of a screening log. For these reasons, we seek a (partial) limited waiver of authorization for the purposes of (1) reviewing medical records to identify potential research subjects and obtain information relevant to the enrollment process; (2) conversing with patients regarding possible enrollment; (3) handling of PHI contained within those records and provided by the potential subjects; and (4) maintaining information in a screening log of patients approached (if applicable).

This limited waiver will apply only to MSK.

8.0 PRETREATMENT EVALUATION

Screening Procedure Outline:

Subjects will have a screening visit with the investigator and team. The following will be assessed:

8.1.1 Eligibility Assessments

- Informed consent signed
- Assurance that inclusion and exclusion criteria are met
- Medical History within 28 days prior to randomization
- Sufficient tumor tissue for required biomarker analysis obtained before start of study from a metastatic lesion or loco-regionally recurrent site of disease.
 - Block or minimum of 3 slides obtained from core, punch, excisional biopsy; FNA insufficient.
 - Archival material is sufficient.
 - Material from bone is not sufficient as PD-L1 IHC cannot be done on bone.

- If no material is available from a metastatic or recurrent site, with permission of the principal investigator, material from the primary site of disease at the time of original diagnosis is acceptable.
- HPV ISH, HPV PCR, p-16 expression testing, or EBER where for oropharynx and nasopharynx primary lesions, respectively. If not done by an outside facility, this should be repeated at the trial site. This testing could have been performed on primary lesion at time of initial diagnosis.

8.1.2 Safety Assessments

- Assessment of Signs and Symptoms within 28 days prior to randomization
- Physical Examination within 28 days prior to randomization
- Physical Measurements: weight within 28 days prior to randomization
- Vital Signs and Oxygen saturation: blood pressure, heart rate, temperature, O2 saturation via pulse oximetry within 28 days prior to randomization
- Performance status within 28 days prior to randomization
- Prior medication collection: data on all prior systemic therapy received to treat HNSCC within 28 days prior to randomization
- Concomitant Medication Collection: obtained within 28 days prior to randomization
- Laboratory Tests (obtained within 28 days prior to randomization)
 - Complete Blood Count
 - Comprehensive Metabolic Panel (AST, ALT, TBili, BUN, Creatinine, Ca, Mg, Na, K, Cl, Glucose, Amylase, Lipase)
 - TSH, Free T4, T3
 - Hepatitis B surface antigen, hepatitis C antibody
- Pregnancy Test within 28 days prior to randomization.

